7.1. Adverse Event Management

Adverse events, which include clinical laboratory test variables, will be monitored and documented from the time of informed consent. Subjects should be instructed to report any adverse event that they experience to the investigator. Investigators should make an assessment for adverse events at each visit and record the event on the appropriate eCRF.

Wherever possible, a specific disease or syndrome rather than individual associated signs and symptoms should be identified by the investigator and recorded on the eCRF.

However, if an observed or reported sign or symptom is not considered a component of a specific disease or syndrome by the investigator, it should be recorded as a separate adverse event on the eCRF. Additionally, the condition that led to a medical or surgical procedure (e.g., surgery, endoscopy, tooth extraction, or transfusion) should be recorded as an adverse event, not the procedure.

Any medical condition already present at screening should not be reported as an adverse event unless the medical condition or signs or symptoms present at baseline changes in severity or seriousness at any time during the study. In this case, it should be reported as an adverse event.

Clinically significant abnormal laboratory or other examination (e.g. electrocardiogram) findings that are detected during the study or are present at screening and significantly worsen during the study should be reported as AEs. The investigator will exercise his or her medical and scientific judgment in deciding whether an abnormal laboratory finding or other abnormal assessment is clinically significant. Clinically significant abnormal laboratory values occurring during the clinical study will be followed until repeat tests return to normal, stabilize, or are no longer clinically significant. Any abnormal test that is determined to be an error does not require reporting as an AE.

Recurrence of CDI is not to be reported as an AE unless hospitalization \geq 24 hours is required to treat it. If a hospitalization of \geq 24 hours is not required, it is to be recorded on the Follow-up eCRF and applicable CDI Form which will be reviewed as a component of the efficacy assessment. If hospitalization \geq 24 hours is required, it is to be reported as an SAE.

Adverse events should be followed until the event resolves or the subject exits the study. Events lasting > 3 months are considered to be chronic in nature.

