Adverse events (n=580 in 94 subjects) were collected by the investigational sites and solicited via subject diary following administration of a study enema. The adverse

events reported were mostly mild-to-moderate in severity (90.8%) and were primarily related to gastrointestinal disorders (41.9%) as would be expected in this population.

Death has been reported in seven (7) subjects at the time of the analysis, none (0) of which were reported as related to the study enemas or procedure. Six (6) of the seven (7) were reported as related to a pre-existing condition. Further, one (1) of the seven (7) subjects died prior to receiving the assigned study treatment.

There were 45 (7.8%) serious adverse events (SAEs) in 26 subjects reported. Of the SAEs only three (3) were reported as possibly related to the study enema. Additionally, of the 345 enemas administered in the study, zero (0) had a report of SAE related to the enema procedure. While 31.1 % of SAEs were reported as related to CDI and 77.8% reported as related to a pre-existing condition. No differences in the rate of adverse events between treatment groups was identified in the number of subjects experiencing an adverse event. Additionally, only five (5) subjects were hospitalized for CDI recurrence during the blinded period, none (0) resulting in ICU admission.

A detailed review of subjects with adverse events relative to the number of exposures to RBX2660 (0-4 exposures) was completed which showed there was no significant increase in the number or rate of adverse events with increased exposure to RBX2660. There were 108 subjects (84.4%) in the safety population who were exposed to RBX2660 with a total of 223 exposures for an average of two (2) exposures per subject.

Analysis of the donor screening process indicated no adverse events subsequent to treatment with RBX2660 were linked to transfer of conditions to a subject from an RBX2660 enema or its constituents.

Overall the safety data indicates that treatment with an RBX2660 enema followed by an additional treatment with RBX2660 if needed due to recurrence of CDI symptoms can be safely administered as it does not increase the risk for adverse events or result in a transfer of donor conditions.

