7.2. Definitions

- Adverse event: an adverse event (AE) is any untoward medical occurrence in a clinical investigation subject associated with the use of IP, which does not necessarily have a causal relationship with the treatment. An adverse event can therefore be any unfavorable and/or unintended sign (including an abnormal laboratory finding), symptom, or disease temporally associated with the use of IP.
 - All adverse events, including observed or volunteered problems, complaints, or symptoms are to be recorded on the eCRF within 10 days of site awareness.
- Adverse reaction: All noxious and unintended responses to IP should be considered an adverse reaction. “Responses” to IP means that a causal

relationship between IP and an adverse event is at least a reasonable possibility, i.e. the relationship cannot be ruled out.

- **Serious adverse event (SAE):** An adverse event or adverse reaction is considered serious if, in the view of either the investigator, Medical Monitor or sponsor, it results in any of the following outcomes:

- Death
 - Life-threatening adverse event

NOTE: An adverse event or adverse reaction is considered “life-threatening” if, in view of either the investigator or Sponsor, its occurrence places the subject at immediate risk of death. It does not include an event that, had it occurred in a more severe form, might have caused death.

- Hospitalization \geq 24 hours or prolongation of an existing hospitalization

NOTE: Any hospital admission with at least one overnight stay will be considered an inpatient hospitalization. An emergency room visit without hospital admission will not be recorded as a serious adverse event (SAE) under this criterion, nor will hospitalization for a procedure scheduled or planned before signing of informed consent. However, unexpected complications and/or prolongation of hospitalization that occur during elective surgery should be recorded as AEs and assessed for seriousness. Admission to the hospital for social or situational reasons (i.e., no place to stay, live too far away to come for hospital visits) will not be considered inpatient hospitalizations.

- Persistent or significant incapacity or substantial disruption of the ability to conduct normal life functions

- Congenital anomaly/birth defect.

- Important medical event

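### Protocol 7.1 gives a CDI recurrence one route into SAE reporting, required hospitalization of at least 24 hours, which conflicts with the wider seriousness criteria in 7.2 and the 24-hour rule in 7.6.1

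*Protocol*

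**What the plan says.** Protocol 7.1 treats recurrence as an efficacy outcome: "Recurrence of CDI is not to be reported as an AE unless hospitalization" of at least 24 hours is needed to treat it. Short of that, "it is to be recorded on the Follow-up eCRF and applicable CDI Form which will be reviewed as a component of the efficacy assessment". The one route it names to an SAE is a required stay of 24 hours or more. No other exception is given.

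Protocol 7.2 defines seriousness more widely: "An adverse event or adverse reaction is considered serious if, in the view of either the investigator, Medical Monitor or sponsor", one of six kinds of outcome results. These are death, threat to life, hospitalization of at least 24 hours or a prolonged stay, incapacity, congenital anomaly, and an important medical event. A note under the hospitalization item adds: "Any hospital admission with at least one overnight stay will be considered an inpatient hospitalization".

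Protocol 7.6.1 requires SAEs to be reported within 24 hours of awareness, and explains that this covers adverse events meeting any of the serious criteria. Section 9.12 repeats the 24-hour limit for SAEs and for suspected adverse reactions, and says nothing particular about CDI recurrence.

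**The concern.** Keeping endpoint events out of AE reporting is an ordinary choice when those events are not serious. Here the exemption is lifted by only one of the seriousness criteria. A recurrence that is serious on another ground is, by the specific instruction in 7.1, not an AE. The SAE definition and the 24-hour clock apply only to AEs or adverse reactions.

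Several safeguards depend on that classification. The Medical Monitor reviews SAEs and events the site reports as related (3.12, 7.10). Screening against the stopping rules starts from reported adverse events (7.12). The SAP tables of serious TEAEs and of TEAEs related to *C. difficile* disease (SAP 7.7.1) are built from AE records. A fatal recurrence entered only on the efficacy forms could be absent from all of these, in a trial where recurrence is a central harm to subjects.

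**Working it through.** The plan gives no figure for this point, so the check is mainly of text. Take a recurrence for which hospitalization of at least 24 hours is not required, and apply each criterion in 7.2:

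| 7.2 criterion | Route to SAE under 7.1 |
|---|---|
| Death | None |
| Threat to life | None |
| Incapacity | None |
| Important medical event | None |
| Prolongation of an existing stay | Not named in 7.1 |
| Overnight admission under 24 hours | Ambiguous: below the threshold in 7.1 and in the 7.2 criterion, but inpatient hospitalization under the 7.2 note |

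Congenital anomaly has no practical bearing on a recurrence.

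The next question is whether other text restores the report. Protocol 2.6 and SAP 6.5.4.2 and 7.7.2.2 count death, septic shock, toxic megacolon, perforation, emergency colectomy and ICU admission. SAP 6.5.4.3 collects CDI hospitalizations. Protocol 6.15 lists death as an exit reason, and 3.8 asks for failures to be entered in the database shortly after determination. None of these sets a 24-hour deadline or makes the event an SAE.

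For scale only, the number of recurrences to which 7.1 applies can be estimated:

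- At the planning success rates of 69% and 47% with 180 and 90 subjects (Protocol 8.1), expected recurrences are 0.31 × 180 + 0.53 × 90 = 55.8 + 47.7 = 103.5, about 104.
- In study 2014-01, "only five (5) subjects were hospitalized for CDI recurrence during the blinded period, none (0) resulting in ICU admission".
- Blinded failures there, from the rates and counts in Protocol 1.5.2: Group A 41 − 25 = 16; Group B 44 − 20 = 24; Group C 42 − 28 = 14, where 28 = 53 − 25. The total is 54.
- From Table 1 of the SAP appendix: 16 + 25 + 17 = 58.
- Hospitalized share: 5/54 = 9.3%, or 5/58 = 8.6%.

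If that share carried over, and all five stays reached 24 hours (the documents do not say), about 103.5 × 49/54 = 94 to 103.5 × 53/58 = 95 recurrences would go only to the efficacy forms. Most would be non-serious and rightly exempt. The documents give no basis for counting those that would be serious on another ground.

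**The case against.** The case for leaving the text alone has substance, and much of it limits the point.

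- **The test is need, not length of stay.** Section 7.1 asks whether hospitalization of at least 24 hours is required. A reader might infer that a subject who arrives in septic shock and dies within hours is exempt. That subject probably did require such hospitalization, so 7.1 probably still captures the case. Death at home is the clear fatal example.
- **Complications are not the exempt event.** Recurrence means CDI diarrhea with a positive toxin test within 8 weeks (3.4, 3.7). Septic shock, toxic megacolon and perforation lie outside that definition and can be reported as their own AEs; Table 7-1 grades some of these consequences. The instruction in 7.1 to record the disease rather than its signs and symptoms leaves some doubt, but it does not mention complications.
- **There are backstops.** Section 7.8 encourages an investigator who is unsure to enter the finding as an AE, 7.11 gives the DSMB a review of efficacy data, and a site following 7.6.1 might report a fatal recurrence anyway. This stands as mitigation. It does not remove the conflict, because 7.1 is the specific instruction for this event and points the other way.
- **Unseen material.** A figure under 7.6 is not shown, and the Safety Management Plan is a separate document. Either could help, but sites should not need them to resolve a contradiction within the protocol.

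A reader might also infer that each such case is a missed expedited report to the regulator. Section 7.13.1 does not support that: the 15-day report needs an event that is serious, unexpected and a suspected adverse reaction, and the 7-day report needs an unexpected, suspected reaction that is fatal or life-threatening. Suspected adverse reactions also have their own 24-hour site rule in 9.12. What the wording puts at risk is the site's SAE report to the sponsor and the reviews that depend on it.

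**Conclusion.** The conflict is real and 7.1 should be corrected. As written, it gives no SAE route to a recurrence that is fatal or life-threatening without required hospitalization of at least 24 hours, or that is an important medical event managed without admission. No text in the two documents restores that route. Separate tabulation of death and major CDI complications keeps them in the final safety account, but not on a 24-hour clock.

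The gap is narrow. The number affected is unknown and probably small. The share of recurrences outside AE reporting, roughly nine in ten on the 2014-01 figures, might be taken as the size of the gap; it is not, because most of those recurrences would be non-serious. Nor should a short overnight admission be read as a clear escape from reporting. The 7.1 threshold agrees with the 7.2 criterion, and the inconsistency is between that criterion and its own note.

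The conclusion rests on a literal reading of 7.1 as the controlling instruction. One further uncertainty remains: Protocol 8.1 calls CDI after 8 weeks a new infection, and 7.1 does not say whether its exemption covers it.

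**What to change.** In Protocol 7.1, replace the hospitalization condition with one stating that a recurrence is exempt from AE reporting unless it meets any seriousness criterion in Section 7.2. Keep the exemption for non-serious recurrences. Add that complications of CDI are recorded as their own conditions. This should name the condition, such as septic shock or perforation, and not the colectomy or ICU admission, because 7.1 already tells sites to record the condition behind a procedure. State whether the exemption also applies to CDI after 8 weeks.

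Separately, reconcile the 24-hour criterion in 7.2 with its overnight-stay note, so that 7.1 and 7.2 use one hospitalization criterion.

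The cost is a few sentences in the protocol, a site memo and a few more SAE forms. No endpoint, sample size or treatment rule changes.

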7.2. Definitions

- Adverse event: an adverse event (AE) is any untoward medical occurrence in a clinical investigation subject associated with the use of IP, which does not necessarily have a causal relationship with the treatment. An adverse event can therefore be any unfavorable and/or unintended sign (including an abnormal laboratory finding), symptom, or disease temporally associated with the use of IP.
 - All adverse events, including observed or volunteered problems, complaints, or symptoms are to be recorded on the eCRF within 10 days of site awareness.
- Adverse reaction: All noxious and unintended responses to IP should be considered an adverse reaction. “Responses” to IP means that a causal

relationship between IP and an adverse event is at least a reasonable possibility, i.e. the relationship cannot be ruled out.

- **Serious adverse event (SAE):** An adverse event or adverse reaction is considered serious if, in the view of either the investigator, Medical Monitor or sponsor, it results in any of the following outcomes:

- Death
 - Life-threatening adverse event

NOTE: An adverse event or adverse reaction is considered “life-threatening” if, in view of either the investigator or Sponsor, its occurrence places the subject at immediate risk of death. It does not include an event that, had it occurred in a more severe form, might have caused death.

- Hospitalization \geq 24 hours or prolongation of an existing hospitalization

NOTE: Any hospital admission with at least one overnight stay will be considered an inpatient hospitalization. An emergency room visit without hospital admission will not be recorded as a serious adverse event (SAE) under this criterion, nor will hospitalization for a procedure scheduled or planned before signing of informed consent. However, unexpected complications and/or prolongation of hospitalization that occur during elective surgery should be recorded as AEs and assessed for seriousness. Admission to the hospital for social or situational reasons (i.e., no place to stay, live too far away to come for hospital visits) will not be considered inpatient hospitalizations.

- Persistent or significant incapacity or substantial disruption of the ability to conduct normal life functions

- Congenital anomaly/birth defect.

- Important medical event

NOTE: Important medical events that may not result in death, be life-threatening, or do require hospitalization may be considered serious when, based upon appropriate medical judgment, they may jeopardize the subject and may require medical or surgical intervention to prevent one of the outcomes above. Examples of such medical events include allergic bronchospasm requiring intensive treatment in an emergency room or at home, blood dyscrasias or convulsions that do not result in inpatient hospitalizations, or the development of drug dependency.

- **Unexpected Adverse Reaction:** An adverse reaction, the nature or severity of which is not consistent with the applicable product information.

- **Unexpected adverse event or unexpected suspected adverse reaction:** An adverse event or suspected adverse reaction is considered “unexpected” if it is not listed in the Investigator’s Brochure or is not listed at the specificity or severity that has been observed.

7.3. Anticipated Adverse Events

The following is list of anticipated adverse events that may or may not be causally related to IP, the enema procedure, or CDI:

- gas (flatulence)
- belching
- abdominal distension or bloating
- increased diarrhea
- abdominal cramping or pain
- constipation
- colitis
- fever $\geq 37.8^{\circ}$ C (100.0°F)
- fatigue
- chills
- transmission of disease from the donor to recipient
- rectal irritation or pain
- rectal bleeding
- nausea
- vomiting
- hypotension
- puncture of the intestine

7.4. Solicited Events

The following list of anticipated events are solicited from subjects via the Subject Diary:

- gas (flatulence)
- abdominal distension or bloating
- rectal irritation or pain
- chills/severe shivering
- abdominal pain or cramping
- increased diarrhea
- constipation
- rectal bleeding
- nausea
- vomiting
- fever $\geq 37.8^{\circ}$ C (100.0°F)

Through the completion of the Subject Diary, subjects are asked specific questions regarding frequency and severity of the solicited AEs.

7.5. Preexisting Condition

A preexisting condition, including abnormal physical exam findings, is one that is present at the start of the study and is to be recorded at the time of the screening visit. A preexisting condition is only to be recorded as an adverse event if the frequency, intensity or the character of the condition worsens during study participation.

7.6. Serious Adverse Event Reporting – Procedures for Investigators

[figure not shown]
7.6.1. Initial Reports

All SAEs occurring from the time of informed consent until 6 months after administration of the last study enema of IP must be reported to Medpace Clinical Safety **within 24 hours** of the knowledge of the occurrence (this refers to any adverse event that meets any of the aforementioned serious criteria). All serious adverse events that the investigator considers related to study drug occurring after 6 months after administration of the last enema of IP must be reported to the Sponsor.

To report the SAE, complete the SAE form electronically in the electronic data capture (EDC) system for the study. When the form is completed, Medpace Safety personnel will be notified electronically and will retrieve the form. If the event meets serious criteria and it is not possible to access the EDC system, send an email to Medpace Safety at [contact] or call the Medpace SAE hotline (phone number listed below), and fax the completed paper SAE form to Medpace (fax number listed below) within 24 hours of awareness. When the EDC system becomes available, the SAE information must be entered within 24 hours of the system becoming available.

Safety Contact Information:
Medpace Clinical Safety

Medpace SAE hotline – USA:

7.6.2. Follow-Up Reports

The investigator must continue to follow the subject until the SAE has subsided or until the condition becomes chronic in nature, stabilizes (in the case of persistent impairment) or the subject dies. Chronic is defined as a condition lasting >3 months.

Within 24 hours of receipt of follow-up information, the investigator must update the SAE form electronically in the EDC system for the study and submit any supporting documentation (e.g., subject discharge summary or autopsy reports) to Medpace Clinical Safety via fax or e-mail. If it is not possible to access the EDC system, refer to the procedures outlined above for initial reporting of SAEs.

7.7. Grading Event Severity

Identified, subject reported and unsolicited adverse events are to be graded, according to severity, by the site investigator. For this classification of events, severity is not the same as seriousness, which is defined in Section 7.1. Severity is an indication of the *intensity* or a specific event (e.g., mild, moderate or severe). Classification of an event as serious relates to an event's outcome or intervention criteria and is usually associated with events that pose a threat to a subject's life or functioning. An event can be severe but not serious, such as a migraine.

Using the definitions in Table 7-1, the site investigator will categorize the severity of a solicited or unsolicited event on the AE eCRF. If a particular event is not listed on this table, the NIH/NCI Common Terminology Criteria for Adverse Events found at online at the following address may be utilized.

https://ctep.cancer.gov/protocolDevelopment/electronic_applications/docs/CTCAE_v5_Quick_Reference_8.5x11.pdf

Table 7-1: Severity Grading Table*

Parameter	Grade 1: Mild	Grade 2: Moderate	Grade 3: Severe	Grade 4: Potentially Life-threatening
Flatulence (gas)	Symptoms causing no or minimal interference with usual social and functional activities	Symptoms causing greater than minimal interference with usual social and functional activities	NA	NA
Belching (burping)	Symptoms causing no or minimal interference with usual social and functional activities	Symptoms causing greater than minimal interference with usual social and functional activities	NA	NA
Abdominal distension or bloating	Symptoms causing no or minimal interference with usual social and functional activities	Symptoms causing greater than minimal interference with usual social and functional activities	Symptoms causing inability to perform usual social and functional activities	NA
Increased diarrhea	Increase of ≤ 3 stools over baseline per 24-hour period	Increase of 4 – 6 stools over baseline per 24-hour period	Bloody diarrhea if not present at baseline OR increase of ≥ 7 stools over baseline per 24-hour	Life-threatening consequences, e.g., hypotensive shock

Parameter	Grade 1: Mild	Grade 2: Moderate	Grade 3: Severe	Grade 4: Potentially Life-threatening
			period OR IV fluid replacement indicated if not indicated at baseline	
Abdominal cramping/pain	Discomfort/pain causing no or minimal interference with usual social and functional activities	Discomfort/pain causing greater than minimal interference with usual social and functional activities	Discomfort/pain causing inability to perform usual social and functional activities	Disabling pain causing inability to perform basic self-care OR inpatient hospitalization \geq 24 hours
Constipation	Occasional or intermittent symptoms, occasional use of stool softeners, laxatives, dietary modifications or enema	Persistent symptoms with regular use of laxatives or enemas indicated	Symptoms causing inability to perform usual social and/or functional activities	Life-threatening consequences, e.g., obstruction, toxic megacolon
Colitis	No symptoms, regardless of pathologic or radiographic evidence of inflammation	Abdominal pain, mucus or blood in the stool	Abdominal pain, fever, change in bowel habits with ileus; peritoneal signs	Life-threatening consequences, e.g., perforation, bleeding, ischemia, necrosis, toxic megacolon
Fever	37.8 – 38.6°C (100.0 – 101.5° F)	38.7 – 39.3°C (101.6 – 102.8° F)	39.4 – 40.5°C (102.9 – 104.9° F)	> 40.5°C (104.9° F)
Fatigue/malaise	Symptoms causing no or minimal interference with usual social and functional activities	Symptoms causing greater than minimal interference with usual social and functional activities	Symptoms causing inability to perform usual social and functional activities	Incapacitating fatigue/malaise symptoms causing inability to perform basic self-care functions
Chills	Symptoms causing no or minimal interference with usual social and functional activities	Symptoms causing greater than minimal interference with usual social and functional activities	Symptoms causing inability to perform usual social and functional activities	NA
Rectal discomfort or irritation	No symptoms or symptoms not	Symptomatic with medical intervention	Symptoms causing inability to perform usual social and	NA

Parameter	Grade 1: Mild	Grade 2: Moderate	Grade 3: Severe	Grade 4: Potentially Life-threatening
	requiring medical intervention	(topical medications / treatments) indicated	functional activities or requiring medical intervention other than topical medications / treatments	
Rectal bleeding	Mild or intermittent without transfusion	Persistent without transfusion	Requires transfusion	Life-threatening consequences
Nausea	Transient (\leq 24 hours) or intermittent nausea with no or minimal interference with oral intake	Persistent nausea resulting in decreased intake for 24-48 hours	Persistent nausea resulting in decreased intake $>$ 48 hours OR aggressive rehydration indicated, e.g., IV fluids	Life-threatening consequence, e.g., hypotensive shock
Vomiting	Transient (\leq 24 hours) or intermittent vomiting with no or minimal interference with oral intake	Frequent episodes of vomiting with no or mild dehydration	Persistent vomiting resulting in orthostatic hypotension OR aggressive rehydration indicated, e.g., IV fluids	Life-threatening consequence, e.g., hypotensive shock
Hypotension	NA	Symptomatic, corrected with oral fluid replacement	Symptomatic, IV fluids indicated	Shock requiring use of vasopressors or mechanical assistance to maintain blood pressure
Adverse event not identified elsewhere in this table	Symptoms causing no or minimal interference with usual social and functional activities	Symptoms causing greater than minimal interference with usual social and functional activities	Symptoms causing inability to perform usual social and functional activities	Symptoms causing inability to perform basic self-care functions OR medical or operative intervention indicated to prevent permanent impairment,

Parameter	Grade 1: Mild	Grade 2: Moderate	Grade 3: Severe	Grade 4: Potentially Life-threatening
				persistent disability, or death

*Adapted from *Division of AIDS Table for Grading of Severity of Adult and Pediatric Adverse Events and Addendum 3: Rectal Grading Table for Use in Microbicide Studies; May 2012*.

